#### **11.4.1. Loading Dose (P2Y12 inhibitor)**

- For subjects who have been taking a P2Y12 inhibitor for  $\geq 72$  hours at the time of the index procedure, a loading dose is not required.
- For subjects who have not been taking a P2Y12 inhibitor for  $\geq 72$  hours at the time of the index procedure, a loading dose is recommended. It is recommended that the loading dose be administered prior to the index procedure or not more than 2 hours after the index procedure. The following loading doses are recommended:
  - Clopidogrel: A peri-procedural loading dose of  $\geq 300$  mg is recommended.
  - Prasugrel: A peri-procedural loading dose of 60 mg is recommended.
  - Ticagrelor: A peri-procedural loading dose of 180 mg is recommended.

#### **11.4.2. Loading Dose (Aspirin)**

- For subjects who have been taking aspirin daily for  $\geq 72$  hours at the time of the index procedure, a loading dose is not required.
- For subjects who have not been taking aspirin daily for  $\geq 72$  hours at the time of the index procedure, a loading dose of aspirin is recommended prior to the index procedure. The dosage of the loading dose is at the discretion of the Investigator. It is recommended that the loading dose be administered prior to the index procedure.

### **11.5. Laboratory Procedures**

If performed per standard of care, results of the following laboratory tests will be recorded in the study electronic data capture system (EDC):

- Before the index procedure (within 72 hours prior to the index procedure), a CK, CK-MB, and/or troponin. If more than one draw was performed within 72 hours, only the most recent value should be recorded in EDC.
- A post-procedural (12 - 24 hours post-index procedure or prior to discharge, if hospitalized < 12 hours) CK, CK-MB, and/or troponin. Only peak enzyme values should be recorded in EDC.

### **11.6. Cardiac Catheterization**

#### **11.6.1. Index Procedure**

The start of the index procedure is defined as the time of sheath insertion. If a previously placed sheath is used (i.e., from a separate diagnostic procedure), index procedure start time is defined as the time of guide catheter insertion into sheath for the interventional procedure.

##### **11.6.1.1. Stent Placement**

Stent placement should be performed per local standard practice. Refer to the DFU for detailed instructions about preparation and placement of the SYNERGY stent.

### **11.7. End of the Index Procedure**

The end of the index procedure is defined as the time the guiding catheter was removed (post final angiography). The introducer(s) sheaths should be removed as per standard local practice.

The following procedures must be completed:

- Document baseline, procedural, target lesion and SYNERGY stent information on the appropriate eCRFs.
- Record antiplatelet medications
- Complete AE assessment and collect source documents as described in Section 20.

### **11.8. Postprocedure/Prehospital Discharge**

- Aspirin: Subjects must be treated with aspirin for the duration of the trial. The minimum daily maintenance dose of aspirin should be 75–100 mg.
- P2Y12 inhibitor: Subjects should be treated with one of the following P2Y12 inhibitors (clopidogrel, prasugrel, or ticagrelor) for 3 months following the index procedure.
- Enrolled subjects must take both aspirin and a P2Y12 inhibitor (clopidogrel, prasugrel, or ticagrelor) for 3 months following the index procedure.

- Enrolled subjects will be evaluated at 3 months to confirm that discontinuation of P2Y12 inhibitor remains appropriate.
- Subjects who are eligible for discontinuation of P2Y12 inhibitor therapy at 3 months are required to take aspirin starting at 3 months and continuing for the duration of the study.
- The subject may be discharged from the hospital when clinically stable at the Investigator's discretion. Generally, this is  $\leq 24$  hours post index procedure but standard, local practice should be followed.
- Complete AE assessment and collect source documents as described in Section 20.
- It is important that trial site personnel review the trial requirements with the subject to maximize compliance with the follow-up schedule and required medication regimen. It is also important that trial site personnel instruct subjects to return/respond for follow-up assessments according to the trial event schedule. Study staff should establish a date for the follow-up visit with the subject and if possible, schedule the visit(s) at the time of hospital discharge.

#### **11.9. Staged Procedures**

- Planned staged procedures are allowed if performed  $\leq 7$  days from the index procedure and with only SYNERGY stents.
- Subjects with a planned staged procedure  $> 7$  days from the index procedure or with stents other than SYNERGY must not be enrolled in the study.
- A staged procedure is only permitted when all enrollment inclusion criteria and no enrollment exclusion criteria are met for all lesions treated during both the initial procedure and the subsequent staged procedure.
- The total number of lesions treated during the index and staged procedures combined must not exceed 3.
- The total number of major epicardial vessels treated during the index and staged procedures combined must not exceed 2.
- In the case of a staged procedure meeting these criteria, the subject should return for the 3-month visit (i.e. assessment for eligibility to discontinue P2Y12 inhibitor) 90 days following the staged procedure + 30 days or - 7 days.

#### **11.10. Follow-Up**

All enrolled subjects who receive a SYNERGY stent will be evaluated in-hospital and at 3 months, 6 months, 12 months and 15 months after the index procedure.

All protocol-required follow-up assessments must be conducted with direct contact with the subjects by a trained study team member, documented on the Delegation of Authority log. In order to allow for flexibility to encourage subject retention, follow-up assessments may be performed via telephone interview or office visit as per local practice. At the time of each protocol required follow-up, study site personnel should answer any study-related questions the subject may have in addition to completing the required protocol assessments.

**11.10.1. 3-Month Follow-up (90 days following the index or staged procedure, if applicable + 30 days or – 7 days)**

All enrolled subjects must be evaluated 3 months after the index or staged (if applicable) procedure. The follow-up assessment may be performed via telephone interview with the subject or during an office visit. During the 3-month follow-up, the following assessments must be completed.

- AE assessment and source document collection as described in Section 20.
- Documentation of current antiplatelet medications (P2Y12 inhibitor and aspirin). Information pertaining to dose changes, medication interruptions (3 days or greater), and medication cessation must be documented.
- Assessment of subject's eligibility to discontinue P2Y12 inhibitor. Investigator involvement in the assessment to discontinue P2Y12 inhibitor is required.
- If a subject meets criteria, the subject should discontinue P2Y12 inhibitor at the time of the 3-month follow-up visit and should continue taking aspirin through the end of the study.

All enrolled subjects should be followed at all milestones through 15-months, regardless of eligibility to discontinue P2Y12 inhibitor

**11.10.1.1. Eligible for Discontinuation of P2Y12 Inhibitor at 3 Months**

Subjects are eligible for discontinuation of P2Y12 inhibitor at 3 months if they meet both of the following criteria:

- Subject was treated with 3 months of P2Y12 inhibitor/aspirin post index procedure. (Subjects enrolled under a prior version of the protocol who were on chronic anticoagulation between 0-3 months are eligible if they were also taking P2Y12 inhibitor or P2Y12 inhibitor/aspirin between 0-3 months).
- Subject was free from events (stroke, MI, PCI, CABG, and stent thrombosis) between the index procedure and the 3-month visit

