## 12. Statistical Considerations

### 12.1. Endpoints

#### 12.1.1. Co-Primary Endpoints

There are two powered co-primary endpoints:

1. The rate of death or myocardial infarction (MI) between 3 and 15 months expressed as the proportion of subjects who experience death/MI between 3 and 15 months among all subjects who either experience death/MI between 3 and 15 months or survive free of death/MI for at least 425 days.
2. The rate of Academic Research Consortium (ARC) definite/probable stent thrombosis (ST) involving SYNERGY between 3 and 15 months expressed as the proportion of subjects who experience ARC ST between 3 and 15 months among all subjects who either experience ARC ST between 3 and 15 months or survive free of ARC ST for at least 425 days.

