#### 12.1.1.2. Sample Size

##### Death/MI:

The expected rate of 5.6% for 3 to 15 month death/MI rates in subjects at high risk for bleeding for both test and control groups is estimated from BSC PROMUS subjects extracted from the HCRI DAPT, PE+ PAS, and PE PROVE studies. The non-inferiority margin is 2.52%, which is 45% of the expected rate. With one-sided 2.5% significance level, the study will require a minimum of 1,500 evaluable subjects per group to provide 85% power to reject the null hypothesis when the alternative hypothesis is true. With consideration of additional 10% subjects accounting for model variability, number of evaluable subjects in the test group required in the propensity score model is 1,650 (1,500 \* 1.1). In the control group, there are approximately 1,643 historical -limus DES high risk for bleeding subjects available from Boston Scientific sponsored trials (403) and the HCRI DAPT Study minus TAXUS (1,240). Assuming that the dropout rate due to the ineligibility between 0 and 3 months for 3-month DAPT test group is 15% and the expected attrition rate between 3 and 15 months is 3%, the study needs to enroll 2,000 subjects in the 3-month DAPT test group.

The enrollment may be terminated earlier if the observed dropout rate between 0 and 3 months is projected to be less than 15%. Enrollment may be continued beyond 2,000 subjects (up to a maximum of 2,250 subjects) if the observed dropout rate in 0 to 3 months is projected to be >15%.

The sample size calculation is based on 2-group test of equivalence in proportions with equal allocation using nQuery Advisor® Version 5.0

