### 12.2.1. Analysis Sets

For the EVOLVE Short DAPT Study, a subject is considered enrolled once an informed consent form has been signed and the subject has received at least one commercial SYNERGY stent. Enrolled subjects must meet all inclusion and no exclusion criteria. The analysis set for the test group includes enrolled subjects who meet criteria for discontinuation of P2Y12 inhibitor and who discontinue P2Y12 inhibitor at 3 months. The analysis set will be used as the test group in the propensity score model.

For the death/MI co-primary endpoint analysis, the EVOLVE Short DAPT-like high risk for bleeding subjects will be extracted from HCRI DAPT, PE+ PAS, and PE PROVE studies to form the historical control group. For the secondary bleeding endpoint analysis, the EVOLVE Short DAPT-like high risk for bleeding subjects will be extracted from HCRI DAPT study only to form the historical control group. Bleeding events were not adjudicated by the CEC in the PE+PAS or the PE-PROVE study.

The EVOLVE Short DAPT-like subjects are defined as subjects who meet the EVOLVE Short DAPT Study inclusion criteria and do not meet any of the following exclusion criteria at the time of the index procedure:

- indication for the index procedure of acute ST elevation MI (STEMI) or Non ST elevation MI (NSTEMI),
- previously treated with intravascular brachytherapy,
- left main target lesion,

- more than 3 lesions treated,
- more than 2 vessels treated,
- bifurcations,
- in-stent restenosis,
- saphenous vein graft,
- TIMI flow 0 (total occlusion) or TIMI flow 1 prior to guide wire crossing, and
- thrombus or possible thrombus present in the target vessel (by visual estimate).

The high risk for bleeding subject set is defined as a set of subjects who meets one or more of the following criteria at the time of enrollment:  $\geq 75$  years of age and, in the opinion of the investigator, the risk of bleeding associated with  $>3$  months of DAPT outweighs the benefit, chronic or lifelong anticoagulation therapy, history of major bleeding (severe/life threatening or moderate bleeding based on the GUSTO classification) within 12 months of the index procedure, stroke (ischemic and hemorrhagic), or renal insufficiency (creatinine  $\geq 2.0$  mg/dl) or failure (dialysis dependent), and platelet count  $\leq 100,000$   $\mu\text{L}$ .

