**Revision History**

Revision Number	Release Date	Section	Change	Reason for Change
			the Bleeding Academic Research Consortium (BARC) classification (types 2, 3 and 5) between 3 and 15 months in subjects not taking chronic anticoagulation.	represented in the DAPT Study control population).
AC to AD	June 20, 2016	Synopsis, Section 11.10	Update to calculation for follow-up windows after 3-months. Windows for 6, 12 and 15 month follow-ups based upon the date of the 3-month visit (representing the date of DAPT discontinuation).	Revisions to allow full year of follow-up in analysis dataset, following the 3-month DAPT discontinuation. Removal of earlier half of 15-month visit ensures full year of follow-up after 3-month visit date.
AC to AD	June 20, 2016	Synopsis, Section 11.8	Addition of “• Enrolled subjects with a need for chronic or lifelong anticoagulation must be treated with a P2Y12 inhibitor (clopidogrel, prasugrel, or ticagrelor) for 3 months following the index procedure, but are not required to take aspirin in addition to the P2Y12 inhibitor between 0-3 months. These subjects may be treated with aspirin between 0-3 months, in addition to the	Clarification of antiplatelet requirements for subjects who are also taking chronic anticoagulants

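### The 3 to 15 month window has no stated start day; if it runs from day 90 after the procedure, late-seen test subjects carry event-free days that controls do not

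*Combined protocol and SAP*

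**What the plan says.** **Entry to the test group.** Section 12.2.1 states: "The analysis set for the test group includes enrolled subjects who meet criteria for discontinuation of P2Y12 inhibitor and who discontinue P2Y12 inhibitor at 3", where the number is in months. Section 11.10.1.1 makes one eligibility condition "Subject was free from events (stroke, MI, PCI, CABG, and stent thrombosis) between the index procedure and the 3-month visit". Section 11.10.1 adds that, if eligible, "the subject should discontinue P2Y12 inhibitor at the time of the 3-month follow-up visit". Being alive at the visit is therefore implied.

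**Timing of that visit.** The synopsis and Section 11.10.1 allow 90 days after the index or staged procedure, plus 30 or minus 7. Staging is allowed up to day 7, so the latest visit is day 120 from the last procedure, or day 127 from index.

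**Endpoint.** Section 12.1.1 defines the death/MI rate as the proportion with an event in the 3 to 15 month window, taken "among all subjects who either experience death/MI between 3 and 15 months or survive free of death/MI for at least 425 days". It names no day on which counting starts or stops. Section 12.1.2 uses the same form for bleeding.

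**Follow-up.** The synopsis and Sections 11.10.2 to 11.10.4 schedule later visits from the 3-month visit date; the 15-month contact falls 365 to 395 days after it. If the 3-month visit was missed, the synopsis sets the 15-month contact at 455 days after the procedure. The reason for the current schedule is in the Revision History (June 2016): "Windows for 6, 12 and 15 month follow-ups based upon the date of the 3-month visit (representing the date of DAPT discontinuation"), so that the analysis data cover a full year after stopping.

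**Controls.** Section 12.2.1 screens them on criteria at the index procedure. It sets no month-3 visit, survival or event-free condition.

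**The concern.** The two groups may not be at risk over the same days. Take a test subject whose visit would fall on day 110 and who has an MI on day 100. That subject fails the eligibility condition and leaves the analysis set. A control with the same MI on day 100 is a counted event if the window opens at day 90. The days from 90 to the visit would then be immortal time in the test group only. They would also be days still on DAPT, inside a window meant to describe the period after stopping it.

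The direction is towards success on the death/MI co-primary. Study success requires both co-primaries, and the comparison is non-randomised, so a construction that lowers only the test rate matters. Asking controls to pass a check at day 90 would not remove it, because the test group's gap runs from day 90 to the actual visit.

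**Working it through.** **1. The plan's own figure.** Inputs from Section 12.1.1.2. Rate: "The expected rate of 5.6% for 3 to 15 month death/MI rates". Margin: 2.52 points, set as 45% of that rate. Size and power: "With one-sided 2.5% significance level, the study will require a minimum of 1,500 evaluable subjects per group to provide 85% power".

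n per group = (1.960 + 1.036)² × 2 × 0.056 × 0.944 / 0.0252² = 1,495, against 1,500 stated. Power at 1,500 per group is 85.1%. Enrolment is 1,650 / (0.85 × 0.97) = 2,001, against 2,000 stated. The plan's figures reproduce.

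**2. Which clock the 425 days fit.**
- From the visit: the last scheduled contact is at most 365 + 30 = 395 days later, so a subject seen on schedule could not reach 425 days.
- From the procedure: 455 − 30 = 425.

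The rule therefore works only from the procedure. A subject seen on day 120 then counts as complete 425 − 120 = 305 days after stopping, short of the full year that the visit schedule was built to provide.

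**3. Size of the gap if events are counted from day 90 to day 455.** The gap for a visit on day v is max(0, v − 90). Visits on days 83 to 90 lose nothing. The documents do not give the distribution of visit days. Assuming visits uniform over the 38 days from 83 to 120, the mean gap is (1 + 2 + … + 30) / 38 = 465 / 38 = 12.2 days.

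**4. Bias and type I error.** Assumptions: constant hazard over 365 days, unadjusted z-test, 1,650 test and 1,643 control subjects (Section 12.1.1.2).

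- Points removed when both true rates are 5.6%: 5.6 × g / 365.
- At the margin the true test rate is 5.6 + 2.52 = 8.12%. The probability of declaring non-inferiority is Φ[(0.0252 − (p_t − 0.056)) / SE − 1.96], with SE = √(p_t(1 − p_t)/1,650 + 0.056 × 0.944/1,643).
- Lower figure: gap days carry the on-DAPT rate, p_t = 0.0812 − 0.056 × g/365.
- Higher figure: gap days carry the test rate, p_t = 0.0812 × (1 − g/365).

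| Gap g (days) | Points removed | Share of 2.52 | Type I error, lower to higher |
|---|---|---|---|
| 0 | 0 | 0% | 2.5% |
| 10 (all visits day 100) | 0.15 | 6% | 3.7% to 4.4% |
| 12.2 (uniform 83 to 120) | 0.19 | 7% | 4.0% to 5.0% |
| 15 (all visits day 105) | 0.23 | 9% | 4.5% to 5.7% |
| 30 (all visits day 120) | 0.46 | 18% | 7.7% to 11.8% |

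For the uniform row, higher figure: p_t = 0.0812 − 0.0027 = 0.0785, SE = 0.00872, and Φ(0.31 − 1.96) = 5.0%. An exponential form instead of the linear one gives 0.18 points and 4.8%.

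**5. Stent thrombosis.** With 1,650 subjects and a 1% goal, the exact test passes at 8 or fewer events: P(X ≤ 8) is 1.6% and P(X ≤ 9) is 3.3%. Gaps of 10 and 15 days move 1.6% to 2.1% and 2.4%, still under 2.5%. With every visit on day 120 it is 3.4%. At the planned 0.4%, the expected events removed are 1,650 × 0.004 × g/365: about 0.2 for 10 days and 0.5 for 30 days.

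**The case against.** A reader might infer that the endpoint is counted from day 90, and so that part of the test window is certainly event-free by construction. The documents do not support that as fact.

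- Section 12.1.1 does not say when counting starts. Section 11.10.1.2 spells out the 0 to 3 month period as ending on the date of the 3-month visit. If the endpoint window opens where that period closes, the gap is zero. The reason recorded for the visit-anchored schedule points the same way.
- The 425 days is a rule for who counts as complete. It does not fix the day on which events begin to count.
- The bias needs both a start at day 90 and an end at day 455. If counting runs from day 90 to the visit plus 365 days, test subjects still have about a year at risk and the bias largely cancels.
- Applying the 8.12% rate to gap days sits badly with describing them as on-DAPT days. The lower type I figures deal with this.
- Section 12.2 refers to a study-specific Statistical Analysis Plan, which may define the window. The text supplied does not.

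All of this stands against the certain reading. It does not remove the narrower point. The one rule that is written, 425 days, cannot be on the visit clock, so it conflicts with the follow-up schedule. Controls have no 3-month visit, so a visit-anchored start leaves their window undefined. On the procedure clock, the error runs in favour of success.

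**Conclusion.** The concern holds in conditional form. The plan leaves time zero of its co-primary window undefined, sets a completeness rule on a different clock from its follow-up, and imposes an event-free condition up to the visit on test subjects alone.

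If events are counted from day 90 to day 455, the bias favours non-inferiority: about 0.19 points and a type I error of about 4 to 5% under constant hazard at 5.6% and uniform visit days. Every visit on day 120 gives 0.46 points and about 8 to 12%. That is an upper bound without staging, not an expectation. If counting starts at the visit and runs 365 days, the bias is zero. The effect on the stent thrombosis test is small.

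The documents do not settle which reading applies. It should be settled in writing before outcomes are analysed, because otherwise the window could be chosen with the data in view.

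**What to change.** In Sections 12.1.1 and 12.1.2:

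- **Test group.** Count events from the 3-month visit (the discontinuation date) through 365 days after it.
- **Controls.** Assign each control a landmark day drawn, within its propensity quintile, from the test group's distribution of days since the procedure. Require the control to be alive and free of MI, stroke, PCI, CABG and stent thrombosis at that day, then count the next 365 days. Requiring survival alone would leave part of the asymmetry in place.
- **Completeness.** Replace the 425-day rule with one measured from the same start day in both groups.
- **Sensitivity analysis.** Pre-specify a common landmark, such as day 120 after the procedure (127 from index if staged). It should not be the main analysis: for a subject seen on day 83 it discards 120 − 83 = 37 days straight after stopping, which are days the study is meant to assess.

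The cost is a wording change and one derived date per subject; the test group's dates are already collected. A few control subjects and events before the landmark drop out, so precision falls slightly. Control follow-up has to reach the landmark plus 365 days (at most 120 + 365 = 485 days from the procedure); the documents do not state its length, so this needs checking. The required sample size does not change, and at 1,650 against 1,643 with no gap the unadjusted power is 88.2%.

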**11.10.1.2. Not Eligible for Discontinuation of P2Y12 Inhibitor at 3 Months**

Subjects are not eligible for discontinuation of P2Y12 inhibitor at 3 months if any of the following criteria are met:

- Subject who experiences a stroke, MI, PCI, CABG and/or stent thrombosis, during the 0-3 month period (between the date of index procedure and the date of the 3-month follow-up visit)
- Subject who is non-compliant with P2Y12 inhibitor or aspirin during the 0-3 month period (between the date of the index procedure and the date of the 3-month follow-up visit). Subjects enrolled under a prior version of the protocol who were on chronic anticoagulation between 0-3 months are not eligible if they were not taking P2Y12 inhibitor or P2Y12 inhibitor/aspirin between 0-3 months.

Non-compliant defined as:

- Taking less than 80% or greater than 120% (subject reported); and/or

- Interruption for 14 or more consecutive days
- Subject judged inappropriate for discontinuation from P2Y12 inhibitor use at 3 months due to another condition requiring chronic P2Y12 inhibitor use

Compliance to the use of P2Y12 inhibitor and aspirin will be ascertained from the subject interview at the 3-month follow-up visit and will be used to determine if the subject is eligible for discontinuation of P2Y12 inhibitor. During the interview, the subject will also be asked about any significant interruptions (3 days or greater) in the prescribed treatment since the last follow-up visit.

Note: All enrolled subjects who receive a SYNERGY stent must be followed at all milestones through 15-months, regardless of eligibility to discontinue P2Y12 inhibitor.

